Through reinforcement of the mind-body connection, Tai Chi may be helpful in relieving chronic abdominal pain associated with IBS-C. The gentle moving meditation involved in Tai Chi practice may influence proper breathing and abdominal wall control in addition to massaging internal organs through movement.

Previous research has suggested that therapies engaging the mind-body connection may have promising effects on functional bowel disorders in general, and on IBS specifically. ^{18, 5} Some mind-body therapies, such as gut-focused hypnotherapy, have already gained approval as an effective treatment in reducing symptoms of IBS. ¹⁹ Similarly to already established mind-body therapies, Tai Chi may positively impact symptoms of IBS-C by changing sensory perception or even calming colonic motility. Tai Chi practice could lead to reduced abdominal distention and improved anxiety and depression scores.

II. Specific Aims

This is a single center pilot study. The purpose of the study is to evaluate the efficacy of Tai Chi practice in reducing symptoms of IBS. Patients who meet the Rome IV criteria for IBS-C and who meet the inclusion criteria will be offered participation in the study. We hypothesize that patients practicing Tai Chi will have reduced symptoms of IBS-C as measured through the Global Assessment of Relief, Irritable Bowel Syndrome Severity Scoring System (IBS-SSS), Irritable Bowel Syndrome Quality of Life (IBS-QOL), Visual Analogue Pain Scale, and abdominal distention. We also hypothesize that daily entries made through the GeoPain app will show a trend toward reduced pain intensity.

III. Subject Selection

This study aims to recruit 24 total subjects to be enrolled at one site, Massachusetts General Hospital. The 24 subjects that this study aims to recruit factors in a dropout rate of 15%, with a final sample size of 20 subjects.

INCLUSION/EXCLUSION CRITERIA:

Inclusion

- 1. Age 18 70 years
- 2. BMI \leq 35
- 3. Rome IV criteria for IBS-C
- 4. Continued IBS-C throughout run-in period
- 5. Compliant with reporting during run-in
- 6. Ability to follow verbal and written instructions
- 7. Ability to record daily patient reported outcomes via RedCap survey
- 8. Ability to use the GeoPain app on a smart phone
- 9. Ability to use Zoom as a platform for conducting study visits virtually
- 10. Ability to respond to 80% of the daily diaries
- 11. Ability to attend at least 7 out of 8 Tai Chi classes
- 12. Informed consent form signed by the subjects

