Every session will include the following components: (1) Tai Chi warm ups with a strong emphasis on balance between strength and flexibility while reviewing Tai Chi principles; (2) Tai Chi breathing with self-massage (3) Tai Chi relaxation with meditation and visualizations (4) Tai Chi form which includes 10 moves from the Yang style Tai Chi (5) Tai Chi drills which are the Tai Chi individual postures practice (6) Tai Chi combination of movements and principles which are part of the Tai Chi philosophy. We will instruct patients to practice at least 30 minutes a day at home throughout the intervention period.

7. Data to be Collected and Timeline for Collection

- a. Primary endpoints
 - 1. IBS-SSS (pre-treatment, halfway point, and at conclusion of study)

b. Secondary endpoints

- 1. Likelihood of continuing treatment (5-point scale, end of study)
- 2. Treatment satisfaction (5-point scale, end of study)
- 3. Global Assessment of Relief and Visual Analogue Pain Scale (pre-treatment and each study visit)
- 4. Change of IBS-QOL, VSI, and HADS (pre-treatment, halfway point, and at conclusion of study)
- 5. For each BM: Bristol stool scale, stool frequency (CSBMs and SBMs; for each BM, during run-in and during study)
- 6. Waist circumference measurements (pre-treatment, halfway point, and at conclusion of study)
- 7. Daily: Bloating Scale, Abdominal Discomfort Scale, Constipation Severity Scale
- 8. Gastrointestinal Symptom Rating Scale-IBS version (GSRS-IBS), Irritable Bowel Syndrome-Behavioral Responses Questionnaire (IBS-BRQ), Fear of Food Questionnaire (FFQ) (pre treatment, study visit 2, and at conclusion of study)
- 9. Leg strength assessment patient (pre-treatment, halfway point, and at conclusion of study)
- 10. Instructor assessment as to confidence that patient has mastered technique (x1 at end of study, 5-point scale)
- 11. Client satisfaction questionnaire and qualitative survey (at conclusion of study)
- 12. Stool for metabolomics, and microbiome (pre-treatment and at conclusion of study)

8. Compliance

- a. Study coordinator will remind subjects of Tai Chi sessions and monitor completion of daily diaries, reports of home practice, and rescue medication use. Subject attendance will be monitored during each Zoom/in-person session by staff-completed attendance forms as well as class sign-in sheets. Number of missed sessions for each subject will be tracked.

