- b. During Run-in Period, subjects must complete 80% of REDCap and GeoPain entries to be considered compliant with reporting and to remain eligible to participate in the study.

b.) Adverse Events

- 1. Definition of adverse events
 - a. An adverse event (AE) is any untoward medical occurrence (sign, symptom, illness, abnormal laboratory value, or other medical event) in a subject, whether or not related to the investigational medical device. This includes events related to the procedures involved (any procedure in the Clinical Investigation Plan).
- 2. A serious adverse event (SAE) is any AE that:
 - a. Led to death
 - b. Resulted in a life-threatening condition
 - c. Resulted in a permanent impairment of a body structure or a body function
 - d. Required inpatient hospitalization or prolongation of existing hospitalization for ≥

- 24 h (elective hospitalizations and/or hospitalizations for treatment of pre-existing conditions that did not worsen from baseline are not considered AEs and should not be reported as SAEs)
- e. Resulted in a medical or surgical intervention to prevent permanent impairment to a body structure or a body function
- f. Led to fetal distress, fetal death or a congenital abnormality, or birth defect
- 3. Adverse event recording, assessment, and reporting procedure
 - a. All AEs regardless of seriousness or relationship to treatment including those occurring during the screening period (after the signature of the Informed Consent Form) are to be recorded in the appropriate electronic CRF.
 - b. AEs reported by subject will be discussed in detail and recorded by the Investigator at each visit. AEs will be collected until 28 days after the last administration of the investigational treatment (i.e., until subject terminates his/her participation in the study).
 - c. The Investigator should specify the date of onset, severity, action taken with respect to the investigational treatment, corrective treatment, outcome, and whether or not there is a reasonable possibility that the AE may have been caused by the investigational treatment.
 - d. Should an AE be reported by a study participant that resides/is located outside the state of Massachusetts and that is determined to have been caused by the investigational treatment, the Investigator will contact the participant's local providers to assess the need for follow-up.
 - e. AEs are graded as follows:

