 Stool will be stored to check for metabalomics that may profile changes between the pre-treatment and treatment sample.
- 2. Microbiome Analysis
 Standard 16s rRNA sequencing for taxonomic identification and metagenomic profiling of the gut microbiome will be performed on stool samples to profile microbiome diversity and changes in microbiome between the pre-treatment and treatment sample.

VII. Biostatistical Analysis

- a.) Endpoint analyses
 - 1. Primary endpoint: IBS-SSS will be compared in a paired fashion for individual patients before and after the intervention using repeated measures t-test.
 - 2. Secondary endpoints: The secondary endpoints (as outlined in section V.a.6.b.) will be compared in a similar fashion.

b.) Power analysis

This is a single-center clinical exploratory pilot investigating the treatment of IBS-C using Tai Chi. As a pilot study, we hope to enroll 24 subjects with a final sample size of 20 subjects. The study will be conducted in two cycles of at least 10 subjects each to facilitate a full classroom size. Based on a previous pilot study involving Tai Chi as treatment for rheumatoid arthritis¹², 20 subjects appears to be a feasible number for detecting a trend toward outcomes that can be investigated in a future larger clinical trial.

VIII. Risks and Discomforts

a.) Tai Chi

Tai Chi is a relatively safe practice that is unlikely to cause injury if done with proper instruction. Caution should be exercised with conditions such as pregnancy, hernia, joint problems, and severe osteoporosis.

b.) Other Possible Risks

Other possible risks and side effects include skin irritation from inadvertently coming in contact with preservatives in the specimen collection materials, breach of confidentiality involving protected health information, and that information about taking part in a metabolic/microbiome study could influence insurance companies or employers regarding the patient's health. Study IDs will be utilized to minimize breaches of confidentiality. Filling out questionnaires could cause patients to feel uncomfortable.

IX. Potential Benefits

- a.) It is hypothesized that Tai Chi may be of benefit in patients with IBS-C. Potential benefits may include a decrease in self-reported abdominal pain/discomfort, straining, bloating, and constipation severity, as well as improved quality of life and symptoms severity.

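### Does one paired before/after rule for all secondary endpoints leave GeoPain, the diary measures and the end-of-study items without a usable analysis?

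*Combined protocol and SAP*

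**What the plan says.** Section VII.a contains the whole efficacy analysis. For the primary endpoint, "IBS-SSS will be compared in a paired fashion for individual patients before and after the intervention using repeated measures t-test". For the rest, "The secondary endpoints (as outlined in section V.a.6.b.) will be compared in a similar fashion".

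The secondary list is in Section V, item 7.b. It has 12 numbered items, which hold 23 separate measures:

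- **Items 3, 4, 6, 8 and 9:** ten scales or measurements taken at visits before and after treatment.
- **Items 5 and 7:** six diary measures (Bristol score, CSBMs, SBMs, bloating, abdominal discomfort, constipation severity). Item 5 gives run-in and the study as collection periods. Item 7 says only that its scales are daily.
- **Items 1, 2, 10 and 11:** likelihood of continuing, treatment satisfaction, the instructor's rating of mastery, and the client satisfaction questionnaire with the qualitative survey. All are collected at the end of the study.
- **Item 12:** stool metabolomics and microbiome, sampled before treatment and at its conclusion.

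GeoPain is not in that list. Section II nevertheless hypothesises that "daily entries made through the GeoPain app will show a trend toward reduced pain intensity", and Section V, item 8.b makes run-in completion a condition of staying in: "subjects must complete 80% of REDCap and GeoPain entries to be considered compliant with reporting". The Schedule of Events shows GeoPain and the diary in run-in, throughout treatment and at Day 77.

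**The concern.** A paired comparison needs one value before and one value after for each person. Against that requirement the secondary rule appears to fail in three ways.

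First, GeoPain carries its own hypothesis and burdens participants daily, yet no analysis is named for it. The Visual Analogue Pain Scale (item 3) is a listed pain endpoint, but it is a different instrument.

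Second, items 1, 2, 10 and 11 have nothing to pair. The Day 77 marks for satisfaction and the instructor assessment are also post-treatment, so they do not help.

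Third, the diary measures have many entries per person and no stated way to reduce them to one number. The before period can be inferred from the two-week run-in; the days that count as after cannot.

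The last point has the most at stake. If the window were chosen once the data were visible, the most favourable one could be reported. Section VII.b says the pilot is meant to show which outcomes deserve a larger trial, and a flattering window could distort that choice. The cross-reference in the secondary sentence also fails to lead to the list: V.a concerns remote conduct, and item 6 describes the intervention.

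**Working it through.** **What the plan lets one reproduce.** The only derived figure is the recruitment target: 20 / (1 − 0.15) = 23.5, rounded up to 24, as Section III states. No alpha, power or effect size is given, so no power figure for a secondary endpoint is at risk.

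**Counts.** End-only items: 1, 2, 10 and 11, so 4 of 12. Diary measures: 3 (item 5) + 3 (item 7) = 6. GeoPain: 14 run-in days + 50 treatment days (Days 0–49) = 64 scheduled entries per person, or 65 with Day 77.

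**Effect of the window.** The documents give no response curve, so three are assumed, each reaching a full change of 1 by Day 49. The table shows the mean of the curve over each candidate window.

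| Assumed curve (d = day) | Days 0–49 | Days 36–49 | Days 43–49 |
|---|---|---|---|
| Linear, d/49 | 24.5/49 = 0.50 | 42.5/49 = 0.87 | 46/49 = 0.94 |
| Complete by Day 21, min(d/21, 1) | (11 + 28)/50 = 0.78 | 1.00 | 1.00 |
| Starts after Day 21, (d − 21)/28 from Day 22 | 14.5/50 = 0.29 | 21.5/28 = 0.77 | 25/28 = 0.89 |

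The widest contrast is 0.29 against 0.89, about threefold. It needs the all-days reading. The rule being extended compares values before and after the intervention, and an average over all of Days 0–49 describes the period during it. Only item 5 gives that reading any footing, for three of the six measures, and there as a statement of when data are collected. Between the two late windows the differences are 46/49 − 42.5/49 = 0.07, then 0, then 25/28 − 21.5/28 = 0.125.

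**Noise of each choice.** With independent daily noise and a 14-day run-in, the standard error of a person's before/after difference, in daily SDs, is:

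- last 14 days: √(1/14 + 1/14) = 0.378
- all 50 days: √(1/14 + 1/50) = 0.302
- last 7 days: √(1/14 + 1/7) = 0.463

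For these three curves, a longer window is more precise and shows no more, and usually less, of the final change. A shorter one does the reverse. The 14-day window costs a factor of 0.378 / 0.302 = 1.25 in standard error against all 50 days. Variation between people in their true change would shrink that ratio further.

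**What an analyst would do with each group.** The ten visit measures and the stool samples have before and after values, so the rule reaches them, given a chosen summary for the stool profiles. The end-only items can only be described, because a before/after test cannot be computed. GeoPain has the same daily structure as the diary and can be summarised the same way. The hypothesis for it is only a trend, which a plot over time or a mean change addresses.

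**The case for a change.** The strongest reply is that calling a study exploratory does not supply an analysis. A hypothesis stated in Section II should be answered somewhere in Section VII. An unwritten window leaves freedom that one line of text would remove, and the data are already being collected. Bloating, discomfort and constipation severity are also named as potential benefits in Section IX, so these are not incidental measures.

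Much of this stands as fact. GeoPain is absent from Section VII, the diary summary is unwritten, and a stated window would be tidier. A similar looseness touches the visit scales, which have both Screening and Day 0 values before treatment, with no word on which is baseline.

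The reply does not show that any stated rule gives a wrong result. Where the paired test does not fit, it cannot be run at all, so it cannot mislead. The obvious remedy, fixing Days 36–49 against run-in, is one defensible window among several, and the documents do not favour it. Applying the run-in's 80% completion mark to an analysis window would borrow an eligibility rule for another purpose. Adding GeoPain to the secondary list is a design preference, and averaging its entries assumes a single intensity score per entry, which the documents do not describe.

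**Conclusion.** No change to the plan follows. The gaps are real, but they are unwritten definitions in a single-arm exploratory pilot with a planned final sample of 20, and an analyst would fill them sensibly. The end-only items carry little risk of false inference. The cross-reference is a numbering slip with only one possible target, because the document has a single secondary list. The choice of diary and GeoPain window is a fair trade-off between precision and closeness to the end of treatment.

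If *after* means late treatment, that choice moves the estimate by at most 12.5 percentage points of the end-of-treatment change between the last 14 and last 7 days. The larger spread, 29% to 78% for the all-days average, depends on treating the whole treatment period as *after*. Both figures rest on assumed curves that are illustrative only; a response that rose and then waned would give different values. The noise figures assume independent daily errors. The IBS-SSS primary analysis is untouched throughout.

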Exclusion

- 1. Unwilling to abstain from participation in Tai Chi (other than that provided for the study) or other mind-body practices (i.e. yoga that is new to regimen) until completion of the study
- 2. Non-English speaking
- 3. Participation in any other clinical trial with active intervention within the last 30 days
- 4. Non-compliance with reporting during run-in period (less than 80% completed REDCap and GeoPain entries)
- 5. Inability to stand without assistance for 20 minutes
- 6. Patients reporting any usage of a prohibited medication during the run-in period
- 7. History of regular opiate or narcotic pain-reliever use
- 8. Current use of prescribed or illicit opioids
- 9. Change in current medication regimen related to GI motility, laxatives, or antidepressants
- 10. Abdominal pain severity of 4 on a 0-4 visual analogue scale, where 4 is the worst possible pain, during pre-screen or run-in
- 11. Severe osteoarthritis
- 12. Severe rheumatoid arthritis
- 13. Severe constipation defined as <1 bowel movement per week without use of laxatives
- 14. History of GI lumen surgery (including gastric bypass) at any time or other GI or abdominal operations within 60 days prior to entry into the study
- 15. History of small bowel resection (except if related to appendectomy)
- 16. Subjects anticipating surgical intervention during the study
- 17. Angina, coronary bypass, or myocardial infarction within 6 months prior to Screening Visit
- 18. Crohn's disease or ulcerative colitis
- 19. History of intestinal stricture (e.g., Crohn's disease)
- 20. BMI >35
- 21. Pregnancy (or positive urine pregnancy test(s) in females of childbearing potential)
- 22. Known history of diabetes (type 1 or 2)
- 23. History of gastroparesis
- 24. History of abdominal radiation treatment
- 25. History of pancreatitis
- 26. History of malabsorption or celiac disease
- 27. History of intestinal obstruction or subjects at high risk of intestinal obstruction including

- suspected small bowel adhesions
- 28. History of human immunodeficiency virus
- 29. History of cancer within the past 5 years (except adequately-treated localized basal cell skin cancer or *in situ* uterine cervical cancer)
- 30. Neurological disorders, metabolic disorders, or other significant disease that would impair their ability to participate in the study

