1. Patients agreeing to participate will sign an informed consent with the study physician or research coordinator at the time of enrollment, after proper informed consent has been provided by the site. Due to COVID-19 restrictions and social distancing, REDCap eConsent will take the place of written documentation of informed consent.

c.) Treatment Assignment

1. All patients will participate in 8 weeks of one-hour Tai Chi sessions once per week.

V. Study Procedures

a) Remote conduct of study visits and procedures

Due to COVID-19 and its restrictions, all eligibility screening and study visits listed below will be performed remotely until restrictions are lifted at the study site. All remote visits will be conducted over Zoom and the visit schedule will not change. All research staff will follow the MGH requirements for using Zoom (Enterprise Zoom as well as Healthcare Zoom- for any study visits involving patient care.) All questionnaires will be administered remotely via REDCap or over the phone. All Zoom link invites will be password protected and emailed by research staff to study participants using Send Secure or unencrypted email, depending on the subject's preference.

b.) Study visits and parameters to be measured

- 1. Eligibility Screen (to be conducted via Healthcare Zoom)
 - a. Obtain informed consent (performed by research staff)
 - b. Collect demographic data (performed by research staff)
 - c. Assessment of sufficient space to perform Tai Chi in-home (performed by research staff)
 - d. Assess inclusion/exclusion criteria (performed by research staff)
 - e. Rome IV questionnaire to screen for IBS-C (performed by research staff)
 - f. Collect medical and surgical history (performed by research staff)
 - g. Collect concomitant medications (performed by research staff)
 - h. Self report of height, weight, and waist measurement (if restrictions are lifted and study visits are being performed on site, vital signs will be recorded) (performed by research staff)
 - i. Perform brief physical examination by study physician
 - j. Visual Analogue Pain Scale (performed by research staff)
 - k. Questionnaires including Global Assessment of Relief, Hospital Anxiety and Depression Scale (HADS), Gastrointestinal Symptom Rating Scale-IBS version (GSRS-IBS), Irritable Bowel Syndrome-Behavioral Responses Questionnaire (IBS-BRQ), Fear of Food Questionnaire (FFQ), Visceral Sensitivity Index (VSI), IBS-SSS, and IBS-QOL(performed by research staff)

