- b.) All subjects will be provided with free parking stickers for each visit and \$50 upon completion of Days 0, 21, and 49 (Visit 2, 5, and 9).

X. Monitoring and Quality Assurance

a.) Good clinical practice

The investigator will ensure that this study is conducted in accordance with the principles of "Good Clinical Practice", as outlined in Title 21 of Code of Federal Regulations (CFR), Part 312, subpart D, "Responsibilities of Sponsors and Investigators"; 21 CFR, part 50, "Protection of Human Subjects"; 21 CFR, part 54, "Financial Disclosure by Clinical Investigators"; 21 CFR, part 56, "Institutional Review Boards"; and 21 CFR, Part 11, "Electronic Records, Electronic Signature", are adhered to.

b.) Institutional review board (IRB) approval

The protocol and any accompanying material to be provided to the patient (such as advertisements, patient information sheets, or descriptions of the study used to obtain informed consent) will be submitted by the investigator to the MGH IRB. Approval from the IRB must be obtained before starting the study and should be documented in a letter to the investigator specifying the protocol number, protocol version, protocol date, documents reviewed, and date on which the committee met and granted approval. Any modifications made to the protocol after receipt of IRB approval must also be submitted to the IRB for approval before implementation.

c.) Informed consent

Due to COVID-19 restrictions and social distancing, consent will be obtained remotely using REDCap eConsent/Paperless consent in place of written informed consent, in accordance with 21 CFR Part 11. The eConsent is equivalent to written consent. The Partners approved

REDCap eConsent template will be used to deliver the approved consent form and obtain an electronic signature from study participants and the principal investigator. All electronic consent documents will be stored in the subject's research record in a password protected, Partners encrypted/secured device.

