Written informed consent, in accordance with 21 CFR Part 50, must be obtained prior to participation in the study when social distancing restrictions are lifted and the study is operating on site. Within the context of the inclusion criteria, a proportion of eligible patients may be exhibiting significant cognitive impairment and the lack of capacity to provide consent. As such, all patients will require surrogate consent by a legally authorized representative. The investigator or staff will determine the appropriate family member-person to contact regarding the study, based on the standard operating procedures of MGH and local and state laws. The signed consent form must remain in the patient's medical chart and must be available for verification at any time.

d.) Liability and insurance

The civil liability of the investigator, the persons instructed by the investigator and the hospital, practice, or institute in which they are employed, and the liability of the financial loss due to personal injury and other damage which may arise as a result of the carrying out of this study are governed by the terms and conditions set forth in the Clinical Trial Agreement and applicable law.

e.) Documentation of study findings

Required information will be entered into the appropriate CRFs. All CRFs are to be completed accurately and promptly and should be updated as needed so they reflect the latest information on the patient's file. All records are to be kept in conformance with applicable guidelines and SOPs. When the study is completed, the investigator must retain the essential documents for as long as needed to comply with regulatory authority, local regulations and sponsor requirements further detailed in Section 10.2.5. The investigator shall notify the sponsor prior to moving or destroying any of the study documents.

f.) Study monitoring

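### Section X.c requires surrogate consent for every patient, which does not follow from its own premise and cannot be reconciled with the participant-signed consent process described elsewhere in the protocol

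*Combined protocol and SAP*

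**What the plan says.** Section X.c (Informed consent) has two paragraphs. The first covers remote conduct: a REDCap eConsent replaces the paper form and is used to "obtain an electronic signature from study participants and the principal investigator". The second opens with written consent once the study operates on site. It then says that, given the inclusion criteria, "a proportion of eligible patients may be exhibiting significant cognitive impairment and the lack of capacity to provide consent", and draws the conclusion that "all patients will require surrogate consent by a legally authorized representative". A third sentence has the investigator or staff identify the family member to contact.

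Elsewhere the participant consents. Inclusion 12 in Section III reads "Informed consent form signed by the subjects". Section IV.b says: "Patients agreeing to participate will sign an informed consent with the study physician or research coordinator at the time of enrollment". Section III.a (recruitment) likewise describes consent obtained from the interested subject.

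On the population, Inclusion 6 requires "Ability to follow verbal and written instructions" and Inclusion 7 "Ability to record daily patient reported outcomes via RedCap survey". Inclusions 8 to 10 add use of the GeoPain app, use of Zoom, and a response to 80% of the daily diaries. Exclusion 30 removes patients with "Neurological disorders, metabolic disorders, or other significant disease that would impair their ability to participate in the study".

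**The concern.** The surrogate sentence is an operative rule, followed by an instruction to staff on how to carry it out. It sets a condition of enrolment that no other part of the protocol provides for. Two things are at stake.

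The first is compliance. Section X.f has monitors verify adherence to the protocol, and section X.k bars changes to the protocol or its conduct without IRB approval. Staff therefore cannot simply set the sentence aside. A participant who signs as section IV.b describes, with no representative involved, has been consented in a way that departs from X.c.

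The second is participant protection. The text imposes a representative on competent adults and at the same time implies that people without capacity are eligible. The protocol describes no capacity assessment and no place for a representative to sign.

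**Working it through.** No formula applies and the plan states no figure to reproduce. The check sets the passages side by side.

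1. **Within X.c.** The premise concerns a proportion of eligible patients; the conclusion covers all of them. If some patients lack capacity, a surrogate might be needed for those patients. Nothing in the premise supports a surrogate for the others.

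2. **X.c against the other consent passages.**

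| Place | Who signs | Representative mentioned? |
|---|---|---|
| Section III, Inclusion 12 | Subject | No |
| Section IV.b | Patient, with study physician or coordinator | No |
| X.c, eConsent paragraph | Participant and principal investigator | No |
| X.c, second paragraph | Legally authorized representative, for all patients | Yes |

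No other part of the document mentions a representative, a surrogate signature or a capacity assessment, so nothing resolves the conflict.

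3. **The premise against the eligibility criteria.** X.c attributes the expected impairment to the inclusion criteria. Those criteria point the other way: Inclusions 6 to 10 demand instruction-following, daily self-report, app and Zoom use, and 80% diary response, and Exclusion 30 removes neurological or other significant disease that impairs participation. Section V.8 adds an 80% reporting rule during run-in. None of these is a formal capacity assessment, but together they leave little room for the population that X.c describes.

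4. **Number affected.** Section III plans 24 subjects. Let k be the number consented on site, so that 24 − k are consented remotely.
   - General reading (all patients, either setting): k + (24 − k) = 24 participants consented by the described process would lack a signature that X.c requires.
   - On-site reading (the rule belongs only to the paragraph it sits in): k participants, with k from 0 to 24. Section V.a makes all visits remote until restrictions lift, so k depends on a date the documents do not give.

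5. **Effect on the statistics.** The 24 enrolled and 20 final subjects, and the paired comparison of IBS-SSS in Section VII, do not use the consent rule as an input. Neither changes.

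**The case against.** Several points can fairly be made for the text.

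*The rule applies on site only.* The surrogate sentences do sit in the paragraph that opens with on-site written consent. This reading removes most of the clash with the eConsent and can bring the number affected down to 0, so it stands as a limit on size. It does not remove the contradiction: the sentence covers all patients, and Inclusion 12 and section IV.b have the subject sign without distinguishing the settings.

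*Both signatures could be collected.* For a competent adult this is possible, since Inclusion 12 does not forbid a second signature. A reader might therefore go too far in inferring that the rule is impossible to follow or that every consent would be invalid. What the documents support is narrower: no dual process is described, and a person who lacks capacity could not validly meet Inclusion 12.

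*Consequences for the data.* A reader might infer that people without capacity would enter and spoil self-reported outcomes. The documents do not support that. X.c changes who consents, while Inclusions 6 to 10, Exclusions 30, 31 and 34 and the run-in reporting rule still apply to everyone. Nor is every outcome self-reported: section V.7 lists an instructor assessment and stool metabolomics and microbiome among the secondary endpoints. Participants are not left wholly to themselves either, since the weekly lessons are instructor-led.

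*Recruitment.* A reader might also infer that the rule would block recruitment. Nothing in the documents shows that; a surrogate for each competent adult would be an added burden, and no more can be said.

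**Conclusion.** The point holds as an internal contradiction in the consent text, and X.c is wrong as written. Its conclusion does not follow from its premise, and it cannot be reconciled with Inclusion 12, section IV.b or the eConsent signatories. Confidence in this is high, because it rests on the wording alone.

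The size is all 24 planned participants on the general reading and 0 to 24 on the on-site reading. This assumes that enrolment reaches the planned 24 and that consent is taken as section IV.b and the eConsent paragraph describe. A flat contrast of all participants under X.c against none under Inclusion 12 would be firmer than the text allows, because the scope of the paragraph is open and Inclusion 12 is silent on representatives.

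The sentences may have been carried over from another protocol. Section X.e cites a Section 10.2.5 that does not exist in this Roman-numbered document, the adverse event section refers to a medical device, and X.i refers to drug accountability. That is an inference, and the verdict does not depend on it. The harm concerns compliance and participant protection; damage to outcome validity is not shown.

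**What to change.** Amend X.c so that the passages agree. Delete the three sentences that run from the remark about cognitive impairment to the choice of family member. State in their place that each participant gives their own consent, by eConsent or in writing when on site, and add capacity to consent as a requirement in Section III.

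If the investigator and the IRB do intend to enrol people who lack capacity, the alternative is to limit surrogate consent to those people, say how capacity is determined, and bring Inclusion 12, section IV.b and the eConsent signatories into line. The documents do not show which policy was intended, so the investigator should confirm it before amending.

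The first option costs one rewritten paragraph, one added eligibility line and IRB approval of the amendment. The second touches more sections. Neither alters the planned sample size or the primary analysis.
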